Table 3	Page 28	Adverse Events Scoring System

List of Figures

Figure 1	Page 15	Study Design Timeline
Figure 2	Page 21	Device components and description
Figure 3	Page 21	Internal Balloon Catheter and External Handheld Magnet
Figure 4	Page 23	Clinical workflow of PUG procedure

Protocol #1801001

List of Abbreviations

AE	Adverse Event
BMI	Body Mass Index
BP	Blood Pressure
CRF	Case Report Form
DSMB	Data Safety Monitoring Board
ECG	Electrocardiogram
EHM	External Handheld Magnet
FDA	United States Food & Drug Administration
GCP	Good Clinical Practice
GI	Gastrointestinal
hCG	Human Chorionic Gonadotropin
HR	Heart Rate
IBC	Internal Balloon Catheter
IR	Interventional Radiology
REB	Research Ethics Board
LAR	Legally Authorized Representative
PEG	Percutaneous Endoscopic Gastrostomy
PUG	Percutaneous Ultrasound Gastrostomy
SAE	Serious Adverse Event

Protocol Synopsis

Protocol #1801001

Protocol	Version 1.0
Title	A single-center, feasibility study to evaluate the use and safety of the Percutaneous Ultrasound Gastrostomy technique
Brief title	Percutaneous Ultrasound Gastrostomy technique
Sponsor	CoapTech
Investigation Type	Medical Device / Procedure
Study Type	Interventional

Protocol #1801001

Purpose and Rationale	
The purpose of this study is to evaluate the performance, safety and tolerability of the Percutaneous Ultrasound Gastrostomy (PUG) procedure that utilizes a novel device in conjunction with widely available ultrasound technology. The CoapTech device consists of a gastric catheter with a balloon enclosing a magnetic bar at its distal end and an external, handheld magnet. The gastric catheter is passed through the mouth and into the stomach. The external magnet is then used to maneuver the balloon to the desired location, with feedback and guidance from real-time ultrasound visualization. With the external magnet coupled, or “coapted”, to the magnet within the gastric tube balloon, the gastric tube balloon will be in place within the stomach pushing it flush against the internal abdominal wall. This allows for complete ultrasound visualization from skin-to-stomach, facilitating safe percutaneous puncture into the stomach and guidewire-assisted placement of the gastrostomy tube.
 
In this study, subjects will have the procedure performed to assess the performance of the device and aspects of the technique as well as determining safety and tolerability. The phased study approach is as follows:
 
 • Phase 1: 5 subjects, performed in specialty suite • Phase 2: up to additional 20 subjects, performed at the bedside (or in specialty suite, if appropriate) • Phase 3: TBD (will require protocol amendment) 
More than 200,000 gastrostomy tubes are placed each year in the United States, and that number is expected to increase as the proportion of the population that is elderly grows (Roche et al 2003, Goldberg et al 2005, Lynch et al 2004). Percutaneous endoscopic gastrostomy (PEG) has become the most common method for placement of a gastrostomy tube. This requires the use of specialized equipment and the availability of physicians specifically trained in this procedure. The CoapTech device and the Percutaneous Ultrasound Gastrostomy (PUG) technique are designed to reduce the need for specialized equipment as well as to reduce the training required to perform the procedure.

------------------------------	--

Primary Objective(s)	To assess the safety and feasibility of gastrostomy tube placement using the PUG technique and the CoapTech device. The primary outcome of interest will be number and severity of device-related adverse events. Any adverse events during the immediate procedural and post-procedural period with a score of 3 or greater ("serious") will be considered unsafe. Of that set, any adverse safety events during the immediate procedural and post-procedural period with a "relatedness to intervention" score of 3 or greater ("probably related") will be considered device-related. See Table 3.
----------------------	---

Secondary Objectives	
 1) While acknowledging that the study is underpowered, to perform a preliminary direct comparison of the following between the PUG placement and a retrospective cohort of matched controls who undergo gastrostomy placement using the percutaneous radiologic gastrostomy (PRG) push gastropexy technique. 
 a) Serious complication rate: a composite rate inclusive of inadvertent puncture of important structures, damage to structures requiring surgical repair and development of infectious complications during the immediate post-procedure period. Important structures are defined a priori as liver, larger blood vessels (that require operative repair or result in significant blood loss in the opinion of the operator), small or large bowel, spleen, etc.. b) Serious adverse events, individually described as: 
 i) Misplacement harm ii) Infection (Sepsis, Peritonitis) iii) Tissue / Organ Damage iv) Requirement for Salvage Surgery and which type(s) v) Other 2) To describe the preliminary rate of other complications during the immediate procedural period between the PUG placement and a historical cohort of matched controls who underwent gastrostomy placement using the PRG technique. 
 a) Tube rupture b) Retained foreign body due to procedure 3) To compare the preliminary cost and operational factors during the immediate procedural period and overall hospital stay between the PUG placement and a retrospective cohort of matched controls who undergo gastrostomy placement using the PRG technique, including:
----------------------	---

	
a) Length of stay after gastrostomy insertion
 
b) Total variable direct costs by cost category (e.g. medications, suite time, etc.)
 
4) To assess preliminary human factors properties through immediate procedural period data including:
 
a) Overall procedure time
 
b) Physician feedback via surveys on usage properties

Study Design	Single-center, non-randomized, non-blinded feasibility and safety pilot study
Population	The study population will consist of male and female patients (≥ 18 years old) admitted to the hospital and in whom it has been determined by the clinical care team that gastrostomy tube placement is indicated for the administration of nutrition or medications.
Comparator	The comparator group will consist of a matched historical cohort of patients who had gastrostomy tube placement performed using the PRG procedure
Inclusion Criteria	
 • Informed consent must be obtained before any study-specific assessment is performed • Male or female ≥ 18 years of age • BMI ≤ 30, AND BMI ≥ 20 • Indication for gastrostomy tube placement determined to be present by the primary clinical care team • Patient determined to be an appropriate candidate for gastrostomy by the study team • Women of childbearing potential must have negative serum or urine pregnancy test during the current hospitalization

Exclusion Criteria	
 • BMI > 30, OR BMI < 20 • Temperature \geq 38 C • Systolic BP < 100 or > 180 mmHg • Heart Rate < 50 or > 110 • Presence of a contraindication to being in proximity to a magnet (e.g. pacemaker). • History of prior gastrostomy, gastrectomy (partial or complete), or abdominal trauma or upper-abdominal surgery. • Patients with hematocrit <25%, or a history of blood transfusion within the 14 days prior to screening, or active life-threatening GI bleeding. • Pregnant or nursing (lactating) women, where pregnancy is defined as the state of a female after conception and until the termination of gestation, confirmed by a positive hCG laboratory test. • Involvement in other investigational trials within 30 days prior to screening. • Any other medical condition(s) that may put the patient at risk or influence study results in the investigator's opinion, or that the investigator deems unsuitable for the study. For example, large or collapsed transverse colon overlapping anterior stomach on pre-existing radiographic scan. • Anticipated discharge <36 hrs from gastrostomy
Investigational and Reference Therapy	
Investigational: Placement of gastrostomy tube using the CoapTech device and the PUG technique
 
Reference: A historical cohort of matched patients who underwent PRG placement.

Efficacy Assessments	
Primary efficacy assessment:
 
Describing the feasibility and safety of gastrostomy tube placement using the PUG technique and the CoapTech device.
 
Key preliminary and secondary efficacy assessments
 
 • Description of occurrences of procedure termination 
 ◦ Termination according to protocol ◦ Termination due to other reasons • Description of any reasons for delays in performance of procedure • Determination of overall rate of any adverse events and relatedness-to-device • Description of occurrences of inadvertent puncture of vital organs during performance of procedure • Description of occurrences of infectious complications • Description of occurrences of salvage surgery performed due to complication of procedure • Description of occurrences of requirements for sedation and analgesia during performance of procedure
Patient Assessments	
 • Physical examination • Vital signs • Height and weight • Calculation of BMI • Abdominal circumference • Laboratory evaluations • Electrocardiogram, if appropriate • Gastrostomy tract depth (measured under ultrasound during procedure)

Other assessments	
 • Preliminary healthcare resource utilization (Costs) 
 ◦ Direct costs of procedure ◦ Environment (e.g. Suite time, etc.) ◦ Laboratory costs ◦ Medication cost ◦ Provider costs ◦ Device costs (estimated) • Length of total ICU and length of total hospital stay after determination made to have gastrostomy tube placed • Indications for gastrostomy placement
Data Analysis	
The primary safety variables are the number and severity of enrolled subjects who have a serious, device-related adverse event during placement of a gastrostomy tube using the PUG procedure.
 
The primary feasibility/efficacy variable is the number of enrolled subjects who have successful placement of a gastrostomy tube using the PUG procedure.
 
Key secondary efficacy variables will be assessed by using common descriptive statistics to a historical cohort of matched subjects who have undergone PRG placement.
 
Data assessments are planned at the end of Phase 1 (n=5), after the 7th subject in Phase 2 (n=12), and at the end of Phase 2 (n≤25).

Introduction

Background

Gastrostomy feeding is an established means of delivering adequate nutrition to patients with an inability to meet their metabolic requirements due to inadequate oral intake. Additionally, the gastrostomy tube can be utilized for medication administration in patients unable to otherwise tolerate oral intake. Traditionally, placement of gastrostomy tubes has been performed endoscopically, radiologically or by either laparoscopic or open surgical techniques. More than 200,000 gastrostomy tubes are placed each year in the United States, and that number is expected to increase as the proportion of the population that is elderly grows (Roche et al 2003, Goldberg et al 2005, Lynch et al 2004).

Previous studies have failed to identify a clearly superior technique for placement of feeding tubes (Bravo 2016, Yuan 2016). Percutaneous endoscopic gastrostomy (PEG) was first described by Gauderer et al. in 1980 in a case series of 12 children as an alternative to laparotomy in high-risk patients (Gauderer 1980). There is a high overall success rate of PEG placement at 95-100% (Itkin 2011). Percutaneous endoscopic gastrostomy (PEG) has become the most common method for placement of a gastrostomy tube. This requires the use of specialized equipment and the availability of physicians specifically trained in this procedure. The number of procedures performed yearly to place feeding tubes is expected to rise as the population ages and as some treatments have resulted in some diseases become chronic states rather than invariably fatal conditions.

Challenges to performance of gastrostomy tube placement include the requirement for specialized equipment, specialized areas designated to have this procedure performed as well as the need for proceduralists who are specifically trained in this technique.

The CoapTech device was developed in an effort to reduce the complicated requirements associated with other techniques of gastrostomy placement so that when clinically indicated the procedure can be performed in a safe and timely manner by a wide range of clinicians with various training backgrounds.

Purpose

This is a single-center, non-randomized, non-blinded feasibility study to evaluate the performance, safety and tolerability of the Percutaneous Ultrasound Gastrostomy (PUG) procedure that utilizes a novel device in conjunction with widely available ultrasound technology. The procedure will be performed in up to 25 eligible subjects. Patients will be followed for 2 days following performance of PUG to assess for potential complications. If the patient remains hospitalized they will be assessed at date of discharge or Day 30 (whichever is earlier) for potential complications.

Study Objectives

Primary Objective

- To assess the feasibility and safety of gastrostomy tube placement using the PUG technique and the CoapTech device. The primary outcome of interest will be number and severity of device-related adverse events. *Any adverse events during the immediate procedural and post-procedural period with a score of 3 or greater (“serious”) will be considered unsafe. Of that set, any adverse safety events during the immediate procedural and post-procedural period with a “relatedness to intervention” score of 3 or greater (“probably related”) will be considered device-related. See Table 3 for scoring system details.*

Key Secondary Objectives

- Description of occurrences of procedure termination
 - Termination according to protocol
 - Termination due to other reasons
- Description of any reasons for delays in performance of procedure
- Determination of categorical rates of serious complications during the immediate procedural period of 48 hours
 - Serious adverse events include but are not limited to the following:
 - inadvertent puncture of important structures
 - damage to structures requiring surgical repair and
 - development of infectious complications.
 - Important structures are defined a priori as liver, larger blood vessels (that require operative repair or result in significant blood loss in the opinion of the operator), or local organs including small or large bowel, spleen, colon, etc.
 - Serious adverse events will be described as:
 - Misplacement harm
 - Infection (Sepsis, Peritonitis)
 - Tissue / Organ Damage
 - Requirement for Salvage Surgery and which type(s)
 - Other
- Description of occurrences of inadvertent puncture of vital organs during performance of procedure

- Description of occurrences of infectious complications
- Description of occurrences of salvage surgery performed due to complication of procedure
- Description of occurrences of requirements for sedation and analgesia during performance of procedure
- Description of reasons for delays in performance of the procedure.

Exploratory Objectives

[figure not shown]
- To evaluate the costs associated with performance of gastrostomy placement using the PUG technique
 - Direct costs of procedure
 - Environment (e.g. Suite time, etc.)
 - Laboratory costs
 - Medication costs
 - Provider costs
 - Equipment costs (other than device)
- Description of length of total ICU and hospital length-of-stay after determination made to have gastrostomy placed
- To assess satisfaction of the clinical care team with the performance of the procedure and human factors of the device.

Investigational Plan

Study Design

After assessing eligibility during the screening period, patients who meet the study inclusion and exclusion criteria will be eligible to have gastrostomy tube placement using the PUG technique with the CoapTech device. Proceduralists who have been trained in the performance of the technique will be contacted to arrange a time to have the procedure performed.

Figure 1. Study Design Timeline

Rationale of Study Design

A single arm, prospective, feasibility and safety pilot study was chosen for this first in-human clinical trial of the PUG procedure. If the study were designed to show reduced rates of complications for the PUG procedure compared to PRG then an unachievable number of subjects would be required to be enrolled. A table was generated demonstrating the number of patients required to show that there is a reduction in complications from 3 to 1%. In order to reject a null hypothesis that there is no reduction in complications of the PUG procedure, 1000 subjects would be required to be enrolled with 500 subjects in each arm of the trial. A trial of this size would not be a reasonable first use in human study. The current study will utilize a matched retrospective cohort of patients who had gastrostomy tube placement performed using the PRG procedure for comparison.

The 25-patient study is divided into two phases. The five patients were selected for phase 1 (n=5) as it should allow for sufficient experience with the PUG technique in a controlled environment that will allow for immediate assessment with fluoroscopy or conversion to PRG if needed. With adequate experience from Phase 1, Phase 2 will then allow for some of the PUG procedures to be performed outside of the interventional radiology suite to assess the unique capability of the PUG procedure.

Table 1. Enrollment Required for Prospective Comparison of PUG vs PEG

Total Patients Enrolled (N)	Patients randomized to PUG	Patients randomized to PEG	Expected # of Serious Complications in PUG patients if true rate = 1%		Expected # of Serious Complications in PEG patients if true rate = 3%		P - value for Null hypothesis PUG rate > PEG rate	
			Complications in PUG patients if true rate = 1%	Complications in PEG patients if true rate = 3%	95% CI for PUG rate	95% CI for PEG rate		
8000	4000	4000	40	120	(0.7% - 1.4%)	(2.5% - 3.6%)	<0.0001	

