The study population will consist of male and female patients (≥ 18 years old) admitted to the participating study site and in whom the primary clinical team has determined that a gastrostomy tube should be placed. The study will focus on patients with a BMI of 20-30 to avoid complications associated with extremes in body habitus.

Inclusion Criteria

Patients eligible for inclusion in this study have to fulfill all of the following criteria:

- Informed consent must be obtained before any study-specific assessment is performed
- Male or female ≥ 18 years of age
- $20 \leq \text{BMI} \leq 30$
- Indication for gastrostomy tube placement determined to be present by the primary clinical care team
- Patient determined to be an appropriate candidate for gastrostomy by the study team
- Women of childbearing potential must have negative serum or urine pregnancy test during the current hospitalization

Exclusion Criteria

Patients fulfilling any of the following criteria are not eligible for inclusion in this study.

- BMI > 30 , or BMI < 20
- Temperature ≥ 38 C
- Systolic BP < 100 or > 180 mmHg
- Heart Rate < 50 or > 110
- Presence of a contraindication to being in proximity to a magnet (e.g. pacemaker).
- History of prior gastrostomy, gastrectomy (partial or complete), or abdominal trauma or upper-abdominal surgery.
- Patients with hematocrit $< 25\%$, or a history of blood transfusion within the 14 days prior to screening, or active life-threatening GI bleeding.
- Pregnant or nursing (lactating) women, where pregnancy is defined as the state of a female after conception and until the termination of gestation, confirmed by a positive hCG laboratory test.
- Involvement in other investigational trials within 30 days prior to screening.
- Any other medical condition(s) that may put the patient at risk or influence study results in the investigator's opinion, or that the investigator deems unsuitable for

the study. For example, large or collapsed transverse colon overlapping anterior stomach on pre-existing radiographic scan.

- Anticipated discharge < 36 hours from gastrostomy.

Method of Assigning Subjects to Treatment Groups

All patients enrolled in the study will have the PUG procedure performed. There is no prospectively enrolled comparator group.

Procedural Team

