Throughout the study, the investigator must record all AEs on the AE CRF, regardless of the severity or relationship to study procedure. The investigator should treat patients with AEs appropriately and observe them at suitable intervals until the events stabilize or resolve. Adverse events may be discovered through observation or examination of the patient, questioning of the patient, complaint by the patient, or by abnormal clinical

laboratory values. In addition, AEs should also include those laboratory values that become out-of-range and are judged to be clinically significant.

Serious Adverse Event (SAE)

A *Serious Adverse Event* is any experience that suggests a significant hazard, contraindication, side effect or precaution. It is any AE that at any dose fulfills at least one of the following criteria:

- is fatal; [results in **death****; NOTE: death is an outcome, not an event]
- is Life-Threatening [NOTE: the term "Life-Threatening" refers to an event in which the patient was at immediate risk of death at the time of the event; it does not refer to an event which could hypothetically have caused a death had it been more severe]
- requires in-patient hospitalization or prolongation of existing hospitalization
- results in persistent or significant disability/incapacity
- is a congenital anomaly/birth defect
- is medically significant or requires intervention to prevent one or other of the outcomes listed above.

Important medical events that may not result in death, be life-threatening, or require hospitalization may be considered an SAE when, based upon appropriate medical judgment, that may jeopardize the patient and may require medical or surgical intervention to prevent one of the outcomes listed in this definition. A life-threatening AE is defined as an AE that placed the patient, in the view of the initial reporter, at immediate risk of death from the AE as it occurred (ie, it does not include an AE that, had it occurred in a more severe form, might have caused death).

Table 3. Adverse Events Scoring System

Pt Identifier	AE Onset	AE End	AE Code (MedRA, CTCAE)	Severity	SAE ? (Y/N)	Related-ness	Action Taken	Outcome	Comments

Severity of AE:

1 = Mild
 2 = Moderate
 3 = Severe
 4 = Life threatening or disabling

Relatedness to Intervention:

0 = Definitely unrelated
 1 = Unlikely
 2 = Possibly related
 3 = Probably related
 4 = Definitely related

Action Taken:

0 = None
1 = Dose modification
2 = Medical intervention
(specify in comments)

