3 = Hospitalization
4 = Intervention discontinued
5 = Other

Outcome:

1 = Resolved
2 = Recovered with minor sequelae
3 = Recovered with major sequelae
4 = Continuing treatment
5 = Condition worsening
6 = Patient death**

Pregnancy Reporting

Pregnancy is an exclusion to enrollment in the current study. If it is determined after enrollment that the study subject is pregnant then all study procedures will be terminated and the Research Ethics Board (REB) will be notified of the protocol deviation. The subject should be followed through the pregnancy for assessment of possible relationship of harm to the study treatment.

Any SAE experienced during pregnancy must be reported to the REB.

Ethical Considerations

This clinical study was designed and shall be implemented and reported in accordance with the ICH Harmonized Tripartite Guidelines for Good Clinical Practice, with applicable local regulations and with the ethical principles laid down in the Declaration of Helsinki.

Research Ethics Board

Before implementing this study, the protocol and the informed consent form must be reviewed by a properly constituted REB. A signed and dated statement that the protocol and informed consent have been approved by the REB must be on file at the site before study initiation. Any amendments to the protocol, other than administrative ones, must be approved by the REB.

If an inspection of the clinical site is requested by a regulatory authority, the investigator must inform CoapTech immediately that this request has been made.

Informed Consent

The Investigator must explain to each participant (or legally authorized representative, LAR) the nature of the study, the purpose, the procedures involved, the expected duration, the potential benefits and risks involved, and any discomfort it may entail. The study procedure should be identified as investigational (experimental) and that its rate of adverse events are not completely known. This information must be provided in

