A single-center, feasibility study to evaluate the use and safety of the Percutaneous
Ultrasound Gastrostomy technique

Principal Investigator:

[name] FRCPC
Division Head for Interventional Radiology
London Health Sciences Centre

NCT03575754

Statistical Analysis Plan

The primary objective of the proposed study is thus the demonstration of safety and feasibility of a novel gastrostomy tube placement (PUG) method using the PUMA-G device in this first-in-human pilot study (n=25). A sample size of 25 was chosen for this study because it provides 80% chance of seeing at least one serious-device related event assuming the event rate is at least 6.3% and a 90% chance of seeing at least one event if the true event rate is at least 11.3%. If no events are observed, then the 95% two-sided upper bound exact binomial CI for the event rate is 13.7%. Hence, the planned sample size has both power to detect at least one event should the event rate be consistent with literature estimates and is sufficient to obtain an upper bound on the event rate of less than 15%; so the planned sample size is considered adequate for this feasibility study. See Table 1 below for calculations.

Table 1: Sample size calculations to optimize ability to detect PUG adverse event

Sample Size	Provides 80% to detect at least one study adverse event if the actual adverse event rate is:	Provides 90% to detect at least one study adverse event if the actual adverse event rate is:	95% One-sided Upper bound for Safety Event Rate	95% Two-sided Upper bound for Safety Event Rate
25	6.3%	8.8%	11.3%	13.7%

It is acknowledged that as a feasibility study, the proposed clinical evaluation is not powered to demonstrate a difference in adverse event outcomes when compared to the standard of care, radiologic gastrostomy tube placement method. In part, this is due to the relatively low rate of complications placement (~4% complication rate). Sample sizes numbering in the thousands would be necessary. These infeasible sample sizes at this stage highlight the need to initially evaluate the PUMA-G device in a feasibility study, per standard development of most medical devices. If successful, further powered studies will be warranted.

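### The primary safety rule labels severity 3 or more as serious, but the protocol defines seriousness separately, so the primary count can omit some SAEs and include some non-SAEs

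*Protocol*

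**What the plan says.** The rule appears twice in the protocol, in the Synopsis (Primary Objective(s)) and in Study Objectives (Primary Objective). It begins "Any adverse events during the immediate procedural and post-procedural period with a score of 3 or greater", labels that set serious and treats it as unsafe. Within that set, events with a relatedness score of 3 or more are called device-related. The body text adds "See Table 3 for scoring system details".

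Table 3 has a severity scale on which 3 is severe and 4 is life threatening or disabling. It has a relatedness scale on which 3 is probably related. It also has a separate yes/no column for SAE. The Serious Adverse Event section just before the table defines an SAE by outcome. One criterion is enough, no severity grade is required, and one of the criteria is that the event "requires in-patient hospitalization or prolongation of existing hospitalization".

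The primary safety variable, in the Synopsis (Data Analysis) and under Efficacy Assessment, is the "number and severity of enrolled subjects who have a serious, device-related adverse event". The SAP bases its sample size on the same event, an "80% chance of seeing at least one serious-device related event". None of these three places says whether serious means the severity threshold or the SAE definition.

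**The concern.** The relatedness half of the rule agrees with Table 3, since code 3 carries the same label in both. The severity half does not: the rule says serious where the table says severe, and the table keeps seriousness in another field. Severity and seriousness are different attributes, and the protocol itself records them separately.

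The study population makes disagreement possible. Every subject is a patient "admitted to the participating study site", so the criterion on prolonging an existing stay can apply to any of them, including after an event graded only moderate.

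At stake is the headline safety figure of a first-in-human study. A reader told how many subjects had a serious, device-related event would reasonably assume the protocol's SAE definition, while the number reported would count severe events. If the meaning is settled only once events are known, the choice could affect the result.

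**Working it through.** **1. Which scale the rule uses.** The sentence before the rule speaks of the number and severity of events, and the sentence after it names relatedness as a second score. The score of 3 or more is therefore taken to be severity.

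**2. Rule against SAE definition.** Take events in the procedural or post-procedural period with relatedness 3 or more:

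| Event | Severity | SAE | Counted by the rule | Serious by the SAE definition |
|---|---|---|---|---|
| Moderate, prolongs the stay | 2 | Y | No | Yes |
| Severe, meets no SAE criterion | 3 | N | Yes | No |
| Severe, prolongs the stay | 3 | Y | Yes | Yes |
| Moderate, meets no SAE criterion | 2 | N | No | No |

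The first two rows disagree, in opposite directions. The first event is also never called device-related under the rule, because relatedness is applied only within the set scoring 3 or more.

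**3. The SAP's own figures (n = 25).**
- Chance of at least one event at a 6.3% rate: 1 − (1 − 0.063)^25 = 80.3%. The SAP says 80%.
- No events, two-sided 95% exact upper bound: 1 − 0.025^(1/25) = 13.72%. The SAP says 13.7%.
- No events, one-sided 95% upper bound: 1 − 0.05^(1/25) = 11.29%. SAP Table 1 says 11.3%.

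**4. One reclassified subject.** The variable counts subjects, so suppose one subject's only device-related event is discordant, there are no others, and all 25 are enrolled. For 1/25 = 4.0%:
- lower limit: 1 − 0.975^(1/25) = 0.10%;
- upper limit: the p that solves (1 − p)^25 + 25p(1 − p)^24 = 0.025, which is 20.35%;
- one-sided 95% upper bound: the same left side set to 0.05, which gives 17.61%.

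| Count | Estimate | Two-sided 95% interval | One-sided 95% upper bound |
|---|---|---|---|
| 0/25 | 0% | 0% to 13.7% | 11.3% |
| 1/25 | 4.0% | 0.1% to 20.4% | 17.6% |

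Reading from the rule to SAE = Y, an event like the first row moves the result down this table, and one like the second row moves it up. The documents give no frequency for either, so no expected shift can be computed.

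**The case against.** The best defence is that the rule is explicit, is stated twice, and sets a threshold for both attributes, so an analyst can compute a count. The primary variable sits in the same protocol and can be taken to inherit that definition, and a short SAP is read together with its protocol. This stands as far as it goes: a count can be produced. It does not remove the conflict, because the rule applies the word serious to a set that differs from the one the protocol's SAE section defines.

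Three stronger readings are tempting, and the documents do not support them.

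- **That SAEs would go unreported or be systematically undercounted.** The secondary objectives describe SAEs by category, including an open other category, and plan rates of serious complications over 48 hours. The Synopsis plans the overall adverse event rate with relatedness, and the DSMB receives all AEs and SAEs. The mismatch also runs both ways. Inpatient status makes prolongation possible, not likely: patients expected to leave within 36 hours are excluded, so some moderate early events could resolve within the planned stay.
- **That the scale is open, since Table 3 also has "3 = Hospitalization" and "3 = Recovered with major sequelae".** Context points to severity, and those lists are not graded: 3 or greater would take in an action coded as other and an outcome coded as continuing treatment.
- **That one event would fail a 15% safety criterion.** The SAP uses 15% only to justify the sample size when no events are seen. No success, stopping or go/no-go rule depends on it.

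It is also fair to say that any rare endpoint at n = 25 moves this much with one event. The avoidable part is that an inconsistent label decides whether the event counts.

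**Conclusion.** The point holds as a conflict between the primary rule and the protocol's own definitions. Followed as written, the serious, device-related count can omit a probably related severity 1 or 2 SAE and can include a severity 3 event that is not an SAE. The number of discordant events is unknown and may be zero, and the net direction is unknown.

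The effect is confined to which events form the primary count and its exact bound. The 0/25 to 1/25 comparison shows what one discordant subject would do and is not a forecast. The conclusion assumes that the score is severity and that severity and SAE status are judged independently, as Table 3's separate columns imply. It should be fixed before analysis. It does not call the design or the safety oversight into question.

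**What to change.** Before analysis, name the Table 3 field that defines the primary event: either severity 3 or more, labelled severe, or SAE = Y, in each case with relatedness 3 or more. Use the same wording in both statements of the primary objective, in both statements of the primary safety variable, and in the SAP.

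Report two numbers side by side, each with its exact confidence interval: subjects with a device-related event of severity 3 or more, and subjects with a device-related SAE. Apply relatedness 3 or more to all events for the second count, not only to those already scoring 3 or more on severity. State in advance which count is primary.

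No new data are needed, because severity, SAE status and relatedness are already Table 3 columns. Keeping the severity rule and relabelling it is a wording change, whereas choosing SAE = Y changes the primary event itself. Either way the cost is a written protocol amendment with its approvals, a matching SAP edit and two counts to present. If SAE = Y is chosen, the primary count may be higher or lower than under the present rule.
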